Osteostar	F-EM	Siemens	7
Duolith SD1 focused	F-EM	Storz Medical	5
Orthospec	F-EH	Medispec (Yehud, Israel)	4
Physio SW Therapy	R	Pagani (Paderno Dugnano, Italy)	3
BTL-5000	R	BTL (Prague, Czech Republic)	2
EvoTron	F-EH	HMT	2
JEST-2000	R	Joemedical (Daejeon, Korea)	2
Masterpuls MP 100	R	Storz Medical	2
Orthima	F-EM	Direx (Petah Tikva, Israel)	2
Piezoon 100	F-PE	Richard Wolf (Knittlingen, Germany)	2
Piezoon 300	F-PE	Richard Wolf	2
Piezowave	F-PE	Richard Wolf	2
Stonelith V5		PCK (Ankara, Turkey)	2
Compact	F-EM	Dornier	1
Duolith SD1 radial	R	Storz Medical	1
Lithostar	F-EM	Siemens	1
MedTech Epos	F-EM	Dornier	1
MFL 5000	F-EH	Phillips (Eindhoven, Netherlands)	1
Masterpuls MP 200	R	Storz Medical	1
Orthowave	F-EH	MTS	1
Piezolith 2501	F-PE	Richard Wolf	1
ShockMaster	R	Gymna (Bilzen, Belgium)	1

R, radial; F-EH, focused-electrohydraulic; F-EM, focused-electromagnetic; F-PE, focused-piezoelectric.

2. Hypothesis

Based on the results of the systematic literature search outlined above it is hypothesized here that rESWT using the Swiss DolorClast is effective and safe in treatment of non-specific low back pain.

Because the majority of patients with non-specific low back pain presenting to the Department of Pain Medicine at the First Affiliated Hospital of Zhejiang University, Hangzhou are suffering from chronic non-specific low back pain, the proposed project will be restricted to the treatment of chronic non-specific low back pain.

The standard therapy of chronic non-specific low back pain at the Department of Pain Medicine at the First Affiliated Hospital of Zhejiang University consists of the non-steroidal anti-inflammatory drug Celecoxib (200 mg per day) and the antispasmodic drug Eperisome (50 mg per day) (henceforth abbreviated to as C-E drug therapy). Considering the established evidence of superiority of combination therapies of rESWT performed with the Swiss DolorClast and other treatment modalities (such as the combination of rESWT and plantar fascia-specific stretching in case of chronic plantar fasciopathy; Rompe et al., 2015; and the combination of rESWT and eccentric loading in case of chronic midportion Achilles tendinopathy; Rompe et al., 2009) the proposed study will specifically test the hypothesis that rESWT performed with the Swiss DolorClast in combination with C-E drug therapy is statistically significantly more effective than either rESWT or C-E drug therapy alone in the treatment of chronic non-specific low back pain.

3. Study Objectives

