4.9. Randomization and blinding of patients

- Patients that fulfill the inclusion criteria and do not fulfill any of the exclusion criteria will be randomly allocated to either rESWT plus C-E drugs (n=50), rESWT alone (n=50) or C-E drugs alone (n=50), respectively (sample size is addressed in Section 5.1. *Power analysis* below).
- Randomization will be performed as described by Rompe et al. (2008) in a randomized, controlled study on rESWT for Achilles tendinopathy. Specifically, a computerized random-number generator will be used to formulate an allocation schedule. Subjects will be randomized to either treatment (rESWT plus C-E drugs, rESWT alone or C-E drugs alone), with use of the method of randomly permuted blocks. The randomization scheme will be generated with the use of the website www.randomization.com. One hundred and fifty patients will be randomized into five blocks. A medical assistant at the Department of Pain Medicine at the First Affiliated Hospital of Zhejiang University will allocate interventions by means of opaque sealed envelopes that will be marked according to the allocation schedule. The medical assistant will be unaware of the size of the blocks.
- The randomized intervention assignment as outlined above will be concealed from both patients and health care staff until recruitment will be complete and irrevocable.

- Neither patients nor therapists will be blinded in the proposed study. The therapist will be the person who will administer rEWST to the patient.
- The assessor will be blinded in the proposed study. The assessor is the person who will assess treatment success during follow up.

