- As outlined in Section "Secondary clinical outcomes" above, the secondary clinical outcomes will be the NRS score, OLDPDQ score, PHQ-9 score, Cobb's angle, vertebral body and intervertebral disc wedging and facet joint angles. Each secondary clinical outcome will return a single data point at each time of follow-up examination. The NRS score, OLDPDQ score and PHQ-9 score are not normally distributed data. Accordingly, we will report inter-quartile ranges of these variables. Comparison between groups will be performed using the nonparametric Kruskal-Wallis test followed by Dunns tests for pairwise comparisons. Normal distribution of the Cobb's angle, vertebral body and intervertebral disc wedging and facet joint angles will be tested using the D'Agostino-Pearson omnibus test. Comparison between groups will be performed with ANOVA followed by Bonferroni post tests for pairwise comparisons in case of passing the normality test, or the nonparametric Kruskal-Wallis test followed by Dunns tests for pairwise comparisons in case of not passing the initial normality test.
- The probability value of less than 0.05 ($p\text{-value} < 0.05$) will be considered as statistically significant (Lang & Secic, 2006).

- All calculations will be performed using GraphPad Prism (version 5.00 for Windows, GraphPad Software, San Diego, CA, USA).
- All main conclusions of the study will be based on analyses of intention to treat rather than analyses of treatment. Note that there are various available methods for handling missing data in clinical trials (European Medicines Agency, 2010). In case of missing data (i.e., in case a patient will withdraw or will be lost during the treatment or the follow-up periods) we will determine together with the statistics experts at the Institute for Medical Informatics, Biometry and Epidemiology (IBE) at the Ludwig-Maximilians-University of Munich (Munich, Germany) the most appropriate method for performing analyses of intention to treat. After randomization and the first treatment with respectively rESWT plus C-E drugs, rESWT alone or C-E drugs alone, no patient will be replaced.
- All efforts will be made to keep the proportion of patients lost to follow-up too small to affect the main findings of the proposed study.
- Patient-centered care throughout the proposed study will ensure that no patients will be lost to follow-up, or the number of patients lost to follow-up will be so small that findings would be unaffected by their inclusion.

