5.1. Power analysis

In none of the studies on ESWT for non-specific low back pain performed so far (Nedelka et al., 2014; Lee et al., 2014; Han et al., 2014; Moon et al., 2016) a definition of treatment success was defined, a Power analysis was reported and the PSEQ score was used to assess clinical outcome. Accordingly, these studies are only of very limited use for the purpose of performing a Power analysis of the proposed study.

Based on anecdotal evidence from several therapists in Europe and Latin America who have been using rESWT for non-specific low back pain for more than a decade we hypothesize that treatment of chronic non-specific low back pain with rESWT alone as described above will result in a success rate of approximately 70%, and the combination of rESWT and C-E drugs in a success rate of approximately 85%. Furthermore, based on our own experience we hypothesize that treatment of chronic non-specific low back pain with C-E drugs alone as described above will result in a success rate of only approximately 35%

On this basis we performed a Power analysis, both for a percentage of 35% as well as for various other percentages (ranging between 10% and 99.9%) of patients with treatment success when treated with C-E drugs alone, accounting for a two sided-confidence interval of 95% (and, thus, a type-1 error rate of 5%). Calculations were performed using the software Open Source Epidemiologic Statistics for Public Health (www.openepi.com). The results are summarized in Tables 7 and 8.

Table 7. Power for the proposed RCT on rESWT plus C-E drugs or rESWT alone for chronic non-specific low back pain, accounting for a two sided-confidence interval of 95% and a percentage of patients with treatment success of 40% when treated with C-E drugs alone (assuming n=50 patients per group).

Percent of patients treated with rESWT plus C-E drugs or C-E drugs alone with treatment success [%]	Power based on Normal approximation [%]	Power based on Normal approximation with continuity correction [%]
99.9	100	100
90	100	100
85	100	100
80	99.8	99.6
70	95.0	92.4
60	71.3	63.5
50	32.7	25.2
40	7.2	3.5
35	1.1	0

Table 8. Power for the proposed RCT on rESWT plus C-E drugs for chronic non-specific low back pain, accounting for a two sided-confidence interval of 95% and a percentage of patients with treatment success of 70% when treated with rESWT alone (assuming n=50 patients per group).

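### For the secondary outcomes, Dunn's test makes combination vs rESWT too conservative when C-E drugs do worse, as the plan expects; a gated two-arm test would avoid this

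*Combined protocol and SAP*

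**What the plan says.** Section 5 states that "The NRS score, OLDPDQ score and PHQ-9 score are not normally distributed data" and therefore prescribes: "Comparison between groups will be performed using the nonparametric Kruskal-Wallis test followed by Dunns tests for pairwise comparisons". The radiographic measures (Cobb's angle, wedging, facet joint angles) are compared by "ANOVA followed by Bonferroni post tests for pairwise comparisons in case of passing the normality test", and by the Kruskal-Wallis and Dunn route otherwise. The threshold is "The probability value of less than 0.05". The plan does not say that pairs are tested only after a significant overall test. It does not spell out the correction inside Dunn's test, and it gives no effect size or power for any secondary outcome.

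Section 2 states the hypothesis that the combination "is statistically significantly more effective than either rESWT or C-E drug therapy alone". Section 5.1 expects rESWT alone to reach a "success rate of approximately 70%, and the combination of rESWT and C-E drugs in a success rate of approximately 85"%, with C-E drugs alone at about 35%. It concludes that the trial is underpowered for combination vs rESWT alone on the primary outcome and treats that contrast as pilot data.

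**The concern.** A pairwise test should ask whether two named arms differ. Dunn's test ranks all 150 patients together and takes its standard error from the case in which all three arms share one distribution. The plan itself expects that case to be false. When C-E patients gather at the poor end of the ranking, the two rESWT arms are squeezed together at the other end while the standard error keeps its full-range value. The result for combination vs rESWT then depends on how badly a third arm does.

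The conventional factor 3 is a second source of conservatism. With exactly three arms it is not needed to hold 5% within an outcome and visit, provided the overall test is a formal gate. The same applies to Bonferroni after ANOVA.

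At stake is one of the two comparisons in the Section 2 hypothesis, on the scales that could add information beyond the primary outcome. P-values for that pair would be larger than a two-arm comparison warrants.

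**Working it through.** **Inputs.** Section 4.9: "rESWT plus C-E drugs (n=50), rESWT alone (n=50) or C-E drugs alone (n=50"). Section 5.1: success of 85%, 70% and 35%, with "accounting for a two sided-confidence interval of 95% (and, thus, a type-1 error rate of 5"%). Assumption: these PSEQ success rates carry over to the secondary scales as unit-SD normal shifts, so combination is 0.51 SD above rESWT and rESWT is 0.91 SD above C-E (differences of the normal quantiles of 0.85, 0.70 and 0.35).

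**The plan's own figure.** Table 8, 85% vs 70%, n = 50, primary outcome:

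Φ{[0.15√50 − 1.96√(2 × 0.775 × 0.225)] / √(0.85 × 0.15 + 0.70 × 0.30)} = Φ{(1.0607 − 1.1575)/0.5809} = Φ(−0.167) = 43.4%, as printed.

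**Dunn's test, approximate.** Write C, R and E for combination, rESWT and C-E.
- P(C>R) = Φ(0.512/√2) = 0.641; P(C>E) = Φ(1.422/√2) = 0.843; P(R>E) = Φ(0.910/√2) = 0.740.
- Expected difference in pooled mean ranks = n{[2P(C>R) − 1] + [P(C>E) − P(R>E)]} = 50 × (0.283 + 0.103) = 19.3.
- Standard error = √[(150 × 151/12) × (2/50)] = √75.5 = 8.69.
- With factor 3 the critical z is 2.394, so the required difference is 2.394 × 8.69 = 20.8. The expected 19.3 falls short. Power ≈ Φ(19.3/8.69 − 2.394) ≈ 43%.
- The third arm's influence: if C-E equals rESWT, the expected difference is 50 × (0.283 + 0.141) = 21.2. If C-E lies entirely below both, it is 50 × 0.283 = 14.1, against the same 20.8.

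**Two-arm Wilcoxon, approximate.** Expected difference 14.1; standard error √[(100 × 101/12) × (2/50)] = 5.80; ratio 2.436. Power ≈ Φ(2.436 − 1.960) = 68% at 0.05 and Φ(2.436 − 2.394) = 52% at 0.05/3, whatever C-E does.

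**Simulation (20,000 trials per scenario), power for combination vs rESWT:**

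| C above R (SD) | E below R (SD) | Dunn | Wilcoxon at 0.05/3 | Gated Wilcoxon at 0.05 | Total loss |
|---|---|---|---|---|---|
| 0.51 | 0.91 (planned rates) | 41.5% | 51.7% | 69.2% | 27.7 |
| 0.51 | 0.5 | 48% | 52% | 70% | 22 |
| 0.51 | 0.3 | 50% | 52% | 69% | 19 |
| 0.51 | 0 | 52% | 52% | 64% | 12 |
| 0.3 | 0.3 | 16% | 17% | 29% | 13 |

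With both shifts at 0.2 SD the loss is about 6 points. With C-E at 40%, the rate in the captions of Tables 7 and 9, power is 44.7% vs 69.9%. On a rounded 0-10 scale at the planned rates it is 41.3% vs 68.7%.

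At the planned rates about 10 points come from pooled ranking (51.7 − 41.5) and about 17.5 from the factor 3 (69.2 − 51.7). At C-E gaps of 0.3 SD or less, pooled ranking costs only 0 to 2 points.

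**Contrasts against C-E at the planned rates.** rESWT vs C-E is 96.6% with Dunn and 99.3% with gated Wilcoxon; combination vs C-E is 100% with both.

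**Error within one outcome and visit.** With three arms, if two pairwise nulls are true then all three arms are equal. So either the global null holds and the gate caps the error at 5%, or at most one pairwise null is true and is tested at 5%. Simulated figures:
- Any false positive with all arms equal: Dunn 4.4%, gated Wilcoxon 4.9%, ungated unadjusted Wilcoxon 12.3%.
- Combination equal to rESWT with C-E worse (70/70/35): Dunn 0.9%, gated Wilcoxon 4.9%.

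**ANOVA route.** Ranks play no part, so only the factor 3 matters: power 56% with Bonferroni vs 72% with gated unadjusted t-tests; error for the truly equal pair 1.7% vs 5.3% (simulation error about 0.25 points).

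**The case against.** Kruskal-Wallis with Dunn and ANOVA with Bonferroni are standard, prespecified and err on the safe side. Several further points stand.

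- **Effect sizes.** PSEQ responder rates need not translate into the same SD shifts on follow-up NRS, OLDPDQ or PHQ-9 scores. The 27 points therefore describe one scenario, and the pooled-rank part nearly vanishes at small gaps.
- **The gate.** The plan says that pairwise tests follow the overall test, not that they depend on it. A reader might infer that the factor 3 is redundant as the plan stands. It is not: without a written gate some correction is needed, as the 12.3% shows.
- **Error control.** A reader might also infer that the conservatism buys nothing at all. That holds only within one outcome and visit. Section 4.11.2 gives NRS and OLDPDQ four follow-ups each and PHQ-9 two, hence ten tests of this pair before the radiographs. If these were independent (an upper-end illustration), the chance of at least one false positive for a truly equal pair would go from 1 − 0.99¹⁰ ≈ 10% to 1 − 0.95¹⁰ ≈ 40%.
- **Disclosure.** Section 5.1 already concedes low power for this contrast on the primary outcome. Pilot data consist mainly of estimates and spread, which the choice of test does not alter.
- **Other properties.** Joint ranking cannot produce circular pairwise orderings, whereas separate Wilcoxon tests can. Bonferroni also allows simultaneous confidence intervals.

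None of this removes the mechanism: under Dunn's test a third arm influences the result for two others.

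**Conclusion.** The point holds as a low-cost improvement to the secondary analysis. If C-E drugs do worse, the planned test is too conservative for combination vs rESWT. Power is about 42% instead of 69% if the 85/70/35% rates carry over as SD shifts, which the documents neither state nor support for the secondary scales. Where the C-E gap is 0.3 SD or less, or the shifts are small, the loss is about 6 to 19 points, mostly from the factor 3. That part also assumes that Dunn's test is run with its conventional correction.

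The documents do not support reading this as a flaw in the trial's main results. The planned tests do not inflate error, the contrasts against C-E lose little at the planned rates, and the primary outcome is tested by Fisher's exact test.

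**What to change.** In Section 5, for the secondary outcomes, replace the Dunn and Bonferroni post tests with text such as: If the overall three-group test (Kruskal-Wallis or ANOVA) has p < 0.05, each pair of groups is compared using only those two groups' data by the Wilcoxon-Mann-Whitney test, or by a t-test with the pooled ANOVA variance where the ANOVA route applies, two-sided at 0.05. If the overall test has p ≥ 0.05, no pair is called significant. With three groups this closed procedure holds the error at 5% within each outcome and visit.

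The gate has to be written out, because the unadjusted tests are not valid without it. The plan should also acknowledge that error across outcomes and visits remains uncontrolled.

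The change needs a short edit to the analysis text and no new patients, visits or data. Its statistical price is a false-positive rate for a truly equal pair of at most 5% instead of about 1% per outcome and visit when C-E is worse, and the loss of simultaneous confidence intervals. If the sponsor prefers no gate, Holm-adjusted two-arm Wilcoxon tests give nearly the same power at the planned rates (69%), but less when the C-E gap is small.

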4.11.2. Secondary clinical outcomes

Secondary clinical outcomes will be:

[figure not shown]
- Numerical Rating Scale (NRS) score - The NRS will ask patients to rate their pain intensity on an 11-point scale where 0 indicates no pain and 10 indicates worst imaginable pain. The NRS score will be collected at baseline and at all follow-up examinations, i.e., two weeks, four weeks, 12 weeks and 24 weeks after baseline. A point score change of 4 points for the NRS score corresponds to the MCID (Maughan and Lewis, 2010). Note that according to

Maughan and Lewis (2010) the NRS score is least responsive in measuring clinically meaningful change in a chronic non-specific low back pain population.

- Oswestry Low Back Pain Disability Questionnaire (OLDPDQ) score (Fairbank and Pynsent, 2000; Davidson and Keating, 2001) – The OLDPDQ score is considered the ‘gold standard’ of low back functional outcome tools. The questionnaire is composed of ten sections (addressing pain intensity, personal care, lifting, walking, sitting, standing, sleeping, sex life, social life and travelling); for each section the possible score is 5 and, thus, the total possible score is 50. The final score is calculated as $[(\text{sum of individual scores}) / 50] * 100$ (%), and is interpreted as *minimal disability* (0% to 20%), *moderate disability* (21% to 40%), *severe disability* (41% to 60%), *crippled* (61% to 80%) or *patients are either bed-bound or exaggerating their symptoms* (81% to 100%). The OLDPDQ score will be collected at baseline and at all follow-up examinations, i.e., two weeks, four weeks, 12 weeks and 24 weeks after baseline. A point score change of 8 points for the OLDPDQ score corresponds to the MCID (Maughan and Lewis, 2010).

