- Patient Health Questionnaire 9 (PHQ-9) score (Kroenke et al., 2001) – The PHQ-9 will be used to assess depression. Patients will be asked how often, over the last two weeks, they had been bothered by the following problems: (i) little interest or pleasure in doing things; (ii) feeling down, depressed or hopeless; (iii) trouble falling or staying asleep, or sleeping too much; (iv) feeling tired or having little energy; (v) poor appetite or overeating; (vi) feeling bad about themselves, or that they are a failure or have let themselves or their family down; (vii) trouble concentrating on things, such as reading the newspaper or watching television; (viii) moving or speaking so slowly that other people could have noticed? Or the opposite – being so fidgety or restless that they have been moving around a lot more than usual; and (ix) thoughts that they would be better off dead or of hurting themselves in some way. For each potential problem the PHQ-9 score uses a 4-point scale where 0 = not at all, 1 = several days, 2 = more than half the days and 3 = nearly every day. The PHQ-9 score will be collected at baseline and at 12 weeks and 24 weeks after baseline.
- Lumbar curvature measurements performed on lateral lumbosacral spine radiographs – Chun et al. (2017) found a strong relationship between non-specific low back pain and decreased lumbar lordotic curvature in a recent meta-analysis based on 13 studies consisting of 796 patients suffering from non-specific low back pain and 927 healthy controls. Lateral X-rays of the lumbar spine will be taken in the standing position according to standard protocols in the literature (e.g., Chernukha et al., 1976; Marks et al., 2009; Been and Kalichman, 2014) and analyzed using Cobb’s angle, vertebral body and intervertebral

disc wedging, and facet joint angle (Fig. 3) (e.g., Been and Kalichman, 2014). Lumbar curvature measurements will be performed at baseline and at 12 weeks after baseline.

Fig. 3 (taken from Been and Kalichman, 2014). Measurements of lumbar lordosis Cobb's angle (LA), vertebral body (B) and intervertebral disc (D) wedging, and facet joint angle (F).

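### Section 5 lets any p below 0.05 count as statistically significant across 14 unranked secondary tests; with no true differences, the chance of at least one false result is up to about 51%, less with correlation.

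*Combined protocol and SAP*

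**What the plan says.** Section 5 states that "the secondary clinical outcomes will be the NRS score, OLDPDQ score, PHQ-9 score, Cobb's angle, vertebral body and intervertebral disc wedging and facet joint angles". It adds: "Each secondary clinical outcome will return a single data point at each time of follow-up examination". For the three questionnaires, "Comparison between groups will be performed using the nonparametric Kruskal-Wallis test followed by Dunns tests for pairwise comparisons". The radiographic measures get ANOVA with Bonferroni post tests, or the same nonparametric route if normality fails.

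Section 4.11.2 gives the visits:

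- "The NRS score will be collected at baseline and at all follow-up examinations, i.e., two weeks, four weeks, 12 weeks and 24 weeks after baseline".
- "The OLDPDQ score will be collected at baseline and at all follow-up examinations, i.e., two weeks, four weeks, 12 weeks and 24 weeks after baseline".
- "The PHQ-9 score will be collected at baseline and at 12 weeks and 24 weeks after baseline".
- The lumbar curvature measurements are taken at baseline and week 12.

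The threshold for declaring significance, "The probability value of less than 0.05", comes directly after the secondary analyses in Section 5 and carries no restriction. Week 12 is singled out only for the primary outcome, PSEQ treatment success. The undertaking in Section 5 to avoid data dredging concerns unplanned subgroup analyses, not planned outcome-by-visit tests.

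**The concern.** Each overall test has a 5% false-positive rate. Because every secondary test may carry the label of statistical significance, the error rate that matters to a reader of the report is the rate for the whole set. The post tests do not help here: they act within one outcome at one visit, after that visit's overall test.

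Two features of this trial make the gap more than a formality. Section 2 hypothesises that the combination beats each component, yet Table 8 gives 43.4% power for 85% against 70% success, and Section 5.1 accepts that the combination versus rESWT alone is underpowered. If that comparison is inconclusive, a set of unranked secondary tests, any of which may be called significant, is a ready substitute. And because no secondary visit has priority, a difference at week 2 or week 24 could be put forward on the same footing as one at week 12.

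This family is separate from the Fisher comparisons of treatment success. Dealing with multiplicity there would leave these 14 tests as they are.

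**Working it through.** **No stated figure to reproduce.** The plan gives no error rate for the secondary outcomes as a set. The only stated rates are the 0.05 threshold in Section 5 and the two-sided 5% used for treatment success in Section 5.1.

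**Count of overall tests (Sections 4.11.2 and 5).**

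| Outcome | Follow-up visits | Tests |
|---|---|---|
| NRS | weeks 2, 4, 12, 24 | 4 |
| OLDPDQ | weeks 2, 4, 12, 24 | 4 |
| PHQ-9 | weeks 12, 24 | 2 |
| Cobb's angle | week 12 | 1 |
| Vertebral body wedging | week 12 | 1 |
| Disc wedging | week 12 | 1 |
| Facet joint angle | week 12 | 1 |
| Total | | 14 |

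This takes each radiographic measure as one number per visit, as Section 5 says.

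**Independent tests, all nulls true.** The chance of at least one p < 0.05 among m tests is 1 − 0.95^m.

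- m = 14: 1 − 0.95^14 = 0.512.
- m = 7 (week 12 only): 1 − 0.95^7 = 0.302.

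**Correlated tests, all nulls true.** The documents give no correlations, so those below are assumptions. The three numbers are the correlation between visits of one questionnaire, between different questionnaires, and among the radiographic measures. Radiographs are taken as uncorrelated with questionnaires. Each test is a three-group comparison, chi-square on 2 degrees of freedom, with 200,000 simulated draws.

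| Assumed correlation | At least one of 14 below 0.05 |
|---|---|
| 0 / 0 / 0 | 51% |
| 0.5 / 0.3 / 0.2 | 45% |
| 0.7 / 0.5 / 0.4 | 39% |
| 0.9 / 0.8 / 0.6 | 28% |

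Simulated Kruskal-Wallis tests with 50 patients per arm agree with these to within about one percentage point. With one common correlation across all 14 tests, the chance is about 44% at 0.3, 35% at 0.5, 26% at 0.7 and 15% at 0.9.

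**Sensitivity of the count.** Section 3.2 lists depression scores at weeks 2 and 4 as well, along with further scores and MRI muscle area that Sections 4.11.2 and 5 do not carry forward. Adding only PHQ-9 at weeks 2 and 4 gives 16 tests, and 1 − 0.95^16 = 0.560 if independent.

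**The case against.** Leaving secondary outcomes unadjusted is common practice, and the plan is clear about what is primary: PSEQ at week 12. The hypotheses that Section 5.1 says the study can test both concern treatment success, and none rests on a secondary outcome. Section 5 also promises actual p-values (except below 0.001), so readers can apply their own adjustment. All of this stands, and it makes the gap one of labelling and permitted claims rather than of design. It does not remove the gap: unadjusted secondary tests are acceptable when called nominal or exploratory, and Section 5 instead calls each result below 0.05 significant.

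Three stronger readings are tempting, and the documents do not support them.

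- A reader might infer that the report would probably contain a false secondary finding. Only full independence takes the chance above one half, and independence is implausible for one scale measured repeatedly in the same patients.
- A reader might take about 40% as a floor. It is not: stronger correlation gives 28% or less, and the documents fix no value.
- A reader might equate these figures with the chance of a false claim for rESWT. A three-group overall test names no arm. Requiring, in addition, a significant Dunn pair favouring an rESWT arm over drugs alone brings the simulated chance to about 18%, 16% and 14% in the first three scenarios of the second table under working (independence, 0.5 / 0.3 / 0.2 and 0.7 / 0.5 / 0.4), the third of these using 0.7 / 0.5 / 0.4. That is well below the overall figures, though still above 5%.

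**Conclusion.** The concern holds as a moderate point. Section 5 permits 14 secondary outcome-by-visit tests, each at 0.05, to be called statistically significant, with no ranking, no adjustment across them and no exploratory label. The resulting chance of at least one false significant overall test is up to about 51%, about 39 to 45% under assumed moderate to high correlations, and about 28% or less under very strong correlation. Even a common correlation of 0.9 leaves about 15%, three times the nominal 5%.

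These figures rest on three conditions: all 14 null hypotheses are true, the count is the one in Sections 4.11.2 and 5, and the correlations are assumed. If the treatments truly differ on some secondary outcomes, fewer nulls are true and the figures fall. The point does not touch the validity of the primary analysis.

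**What to change.** In Section 5, limit the 0.05 rule to the primary outcome, PSEQ treatment success at week 12. (Section 4.11.1 puts the success threshold in points and Section 5 in percent; that needs reconciling separately.) Then add a sentence to this effect: secondary outcomes are reported at each visit as between-group estimates with confidence intervals and nominal p-values, and no claim of statistical significance is based on them.

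Optionally, if the sponsor wants confirmatory secondary claims, restrict them to week 12 and apply Holm at a two-sided family level of 0.05 over the seven week-12 overall tests. The smallest p-value is then compared with 0.05/7 = 0.0071. Pairwise post tests are read only for outcomes that pass, and at the same adjusted level. Whether scales and spinal angles belong in one family is a matter of judgement, which is why this part is optional.

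The cost is one or two sentences in Section 5, with no added patients, visits or data. The downside is fewer or weaker secondary claims.
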